7.2 AMENDMENT H

The sub-aim of Aim 1 was to determine the accuracy of ⁶⁸Ga-DOTATATE to detect unknown primary NETs. However, the current study is under-powered to achieve the first aim in detecting a 20% difference in detection rate between the two imaging modalities (⁶⁸Ga-DOTATATE and CT scan). Of 290 patients accrued to the study, as of amendment G, twenty-one had unknown primary NETs. Under the current accrual trend, assuming a total of 25 patients in the entire cohort have unknown primary 40% of whom were identified by ⁶⁸Ga-DOTATATE. Assuming the proportion of discordant imaging result is 24%. The current study would have only 50% power to detect a 20% difference using McNemar's chi-squared test at the 5% significance level. In order to achieve 90% power, the number of patients with unknown primary NETs need be increased to 55 subjects total (34 excluding those already enrolled).

To date, 24 patients accrued in the current study, as of amendment G, underwent radio-guided surgery with a total of 56 lesions detected on histology. Based on the preliminary data, lesion-

Abbreviated Title: ⁶⁸Gallium Detecting Tumors

Version Date: 09/20/17

based detection rate of DOTATATE gamma probe and CT scan/operative visualization was 71% and 57%, respectively. Assume on average 2 lesions per patient are identified by histology. The variance of the difference in detection rate between the two imaging guided procedures is given by

$$\text{Var}(\hat{P}_1 - \hat{P}_2) = n^{-1}(V_1 + V_2)[1 + (k - 1)r_1] - 2n^{-1}r_2\sqrt{V_1 V_2}$$

$$= \frac{\sigma^2}{n}$$

, where $V_i = \frac{P_i(1-P_i)}{k}$, P_i = true detection rate(i=1 for DOTATATE gamma probe and i=2 for CT

scan), \hat{P}_i = estimated detection rate , k = number of lesions per patient on average, r_1 = inter-lesion correlation, r_2 = intra-lesion correlation between the , and n = number of patients. Based on prior studies, inter-lesion correlation arising from multiple lesions of the same patient is set at 0.2 and intra-lesion correlation between DOTATATE and CT is set at 0.5. With these values and assuming $P1=0.72$ and $P2=0.57$, $\sigma=0.40$. To achieve 90% power in detecting 15% difference in detection rate between the two imaging modalities, with $\sigma=0.40$ a total of 85 patients (including the 24 patients already enrolled) are required using a two-sided Z-test at the 5% significance level.

Therefore, we are increasing our accrual ceiling to 390 patients.

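### Section 7.2 derives the 390 ceiling from two 90%-power targets, but at the study's own rates 390 yields about 28-30 unknown primaries against the 55 required (power roughly 59-69%), and the 85 surgery patients do not follow from the stated 15 points with sigma 0.40

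*Combined protocol and SAP*

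**What the plan says.** Section 7.1 (Amendment D) set the accrual ceiling at 295. Section 7.2 (Amendment H) raises it for two comparisons.

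- Unknown primaries, described as a sub-aim of Aim 1. The count so far: "Of 290 patients accrued to the study, as of amendment G, twenty-one had unknown primary NETs". The projection: "Under the current accrual trend, assuming a total of 25 patients in the entire cohort have unknown primary". At 25 patients, 24% discordance and a 20-point difference, the section states 50% power with McNemar's chi-squared test at the 5% level. For 90% power, "the number of patients with unknown primary NETs need be increased to 55 subjects total (34 excluding those already enrolled").
- Radio-guided surgery. "To date, 24 patients accrued in the current study, as of amendment G, underwent radio-guided surgery", and the preliminary lesion-level comparison is given as "based detection rate of DOTATATE gamma probe and CT scan/operative visualization was 71% and 57%, respectively". A variance formula with planning rates 0.72 and 0.57 gives sigma = 0.40. The requirement is then stated in two parts: "To achieve 90% power in detecting 15% difference in detection rate between the two imaging modalities", and "a total of 85 patients (including the 24 patients already enrolled) are required using a two-sided Z-test at the 5% significance level".

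The closing sentence is "Therefore, we are increasing our accrual ceiling to 390 patients". Section 2.1.1 still admits any patient with imaging suspicion, biochemical evidence, or MEN1/VHL predisposition. Section 2.1.3 lists only website postings as recruitment. No visible section reserves places for either target group.

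**The concern.** The two sample sizes are the only reason 7.2 gives for the new ceiling, so a reader will take 390 as enough for both. That holds only if nearly every added place goes to a patient in one of the target groups. Section 7.2 uses the accrual trend to show that the old ceiling was under-powered for unknown primaries, but does not carry the trend to the new one.

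Detecting unknown primaries is part of the primary objective in 1.1.1. If far fewer than 55 accrue, a non-significant result could be read as no difference between PET/CT and CT when the comparison had little chance of showing one.

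The surgery target raises a second, separate question: whether 85 follows from the inputs printed beside it.

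**Working it through.** **1. The ceiling.** New unknown primaries: 55 - 21 = 34. New surgery patients: 85 - 24 = 61. 295 + 34 + 61 = 390. The plan does not print this sum, so it is an inference, but it matches exactly and allows nothing for patients in neither group.

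**2. Unknown-primary yield at 390.** Places left: 390 - 290 = 100. Reaching 55 needs 34 of those 100 (34%), against 21/290 = 7.2% so far.

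- At 21/290: 21 + 100 × 21/290 = 28.2.
- At 25/295 (reading the plan's entire cohort as the old ceiling): 21 + 100 × 25/295 = 29.5.
- Accepting the assumed 25 at 295 as already reached and scaling it: 390 × 25/295 = 33.1. This needs 4 of the next 5 patients to be unknown primaries.

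The binomial chance of 34 or more in 100 is below 1e-12 at either rate. At 21/290, reaching 55 would take about 55 × 290/21 = 760 patients in total.

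**3. Power for unknown primaries.** Inputs from 7.2: difference 0.20 and discordance 0.24, so the discordant cells are 0.22 and 0.02; 5% level, taken as two-sided. The Connor formula is Φ[(0.20√n - 1.96√0.24)/√(0.24 - 0.04)]. The other two columns enumerate the binomial distribution of the discordant pairs.

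| n | Connor | mid-p | uncorrected chi-squared |
|---|---|---|---|
| 25 (plan states 50%) | 53.5% | 50.8% | 60.1% |
| 28 | 58.7% | 58.8% | 65.4% |
| 30 | 61.9% | 63.4% | 68.5% |
| 33 | 66.4% | 69.5% | 72.8% |
| 55 (plan states 90%) | 87.9% | 92.2% | 92.3% |

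Of these, mid-p reproduces the plan's 50% at n = 25. All three give 88-92% at 55, so 55 is about right as a requirement. At 28-30 they span 59% to 69%; the maximum at 33 is 73%.

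**4. The surgery target.** The plan's formula with k = 2, r1 = 0.2, r2 = 0.5:

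- At 0.72 and 0.57: V1 = 0.1008, V2 = 0.12255; σ² = (V1 + V2) × 1.2 - 2 × 0.5 × √(V1·V2) = 0.1569; σ = 0.396, consistent with the stated 0.40.
- Two-sided 5%, 90% power, 15 points, σ = 0.40: n = (1.96 + 1.2816)² × 0.16/0.15² = 74.7, so 75. With unrounded σ it is 73.3. The stated 85 is not reproduced.
- At the observed 0.71 and 0.57 (14 points): σ = 0.3978; n = (3.2415)² × 0.3978²/0.14² = 84.9. This reproduces 85.
- Power of 85 at 15 points: Φ(0.15√85/0.40 - 1.96) = 93%.

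**5. Surgery yield.** At the rate to date: 24 + 100 × 24/290 = 32.3. Power at 32 for 15 points: Φ(0.15√32/0.40 - 1.96) = 56%. This counts no later operations in patients already enrolled.

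**The case against.** A ceiling is a cap, not a promise. The 55 and 85 are conditional statements of what 90% power requires, the sum behind 390 is never printed, and one patient could count toward both targets. Recruitment could also be directed at unknown primaries. Part of this stands: the sum is an inference. But 7.2 moves from the two requirements to 390 with a therefore, which implies sufficiency, and no targeted recruitment is described. Overlap between the groups would free places without raising the unknown-primary rate.

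The counts are also a snapshot as of Amendment G, while the current version is dated 09/20/17 and section 9.6.5 refers to Amendment J. That stands, and is a reason to use current counts.

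Four stronger readings are tempting, and the documents do not support them.

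- A reader might infer that the surgery comparison is bound to fall short. Patients are followed yearly for five years (Précis), section 3.4.1 allows for surgery when a lesion enlarges, and section 7 expects 10-30% to need an operation. The yield is uncertain, not shown to fail.
- A reader might infer that 85 is too small. It exceeds the 75 needed for the stated inputs.
- A reader might infer that 55 is wrong. It gives close to 90% power on the versions tried.
- A reader might infer that the 295-patient PET/CT versus CT comparison in 7.1 is weakened. It is not affected.

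**Conclusion.** Section 7.2 is wrong as written on two counts.

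First, 390 is presented as following from a 90%-power requirement that it is not expected to meet for unknown primaries. About 28-30 are expected against 55. Power is 59-62% (Connor), 59-63% (mid-p) or 65-69% (uncorrected chi-squared), and at most 73% if 33 are reached. A true 20-point difference would therefore be missed about 31-41% of the time at 28-30. This assumes that the remaining 100 places fill at about the rate seen so far and that the plan's own 20-point difference and 24% discordance hold.

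Second, the stated surgery inputs give 75, not 85. The printed number belongs to a 14-point difference. This errs on the safe side and is a matter of consistency.

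The surgery yield at 390 stays open because 7.2 states no operation rate. The rate to date gives about 32 operations and 56% power, before any later operations in enrolled patients.

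**What to change.** Change the wording of 7.2 only.

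1. Keep 55 as the conditional requirement. Beside it, state the unknown-primary yield and power expected at 390, using one named McNemar version and current counts. On the Amendment G counts this is about 28-30 patients and, with mid-p for example, 59-63%. Do not present 390 as delivering 90% power for this comparison.
2. Reconcile the surgery inputs: either 75 patients for 15 points with sigma 0.40, or 85 patients for 14 points (71% versus 57%). With 75, the same sum is 295 + 34 + 51 = 380, so 390 leaves a margin of 10.
3. State the operation rate assumed for the surgery target, and give the power at the rate to date (about 32 operations, 56%), noting that operations during follow-up may add to this.

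The ceiling, eligibility and procedures do not change. The cost is a less favourable stated power, and the shortfall in unknown primaries is disclosed rather than removed.

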7.3 DETAILED ANALYSIS

We recently performed an analysis of the detection rate of the 3 imaging modalities in the first 131 patients enrolled in the study for known or suspected gastrointestinal and pancreatic neuroendocrine tumors. Lesions detected on any of the 3 imaging modalities were defined as the denominator. ⁶⁸Gallium-DOTATATE detected 95.1% of lesions compared to Octreoscan SPECT, which only detected 30.9% of lesions ($p<0.0001$). Furthermore, in four out of 14 patients, ⁶⁸Gallium-DOTATATE PET/CT found a previously unknown primary tumor not detected by Octreoscan SPECT. Twenty-five patients underwent surgical resection for their primary tumors and/or metastases. An analysis of imaging concordance with histopathology showed that ⁶⁸Gallium-DOTATATE PET/CT found true-positive lesions 63.7% (72 out of 113 lesions) compared to 22.1% (25 out of 113 lesions) for Octreoscan. In assessing the impact of ⁶⁸Gallium-DOTATATE PET/CT on clinical management, ⁶⁸Gallium-DOTATATE PET/CT detected additional lesions in 93 out of the 131 patients (71.0%) compared to Octreoscan SPECT. Forty-four out of the 93 patients with additional lesions were found to have metastatic disease. These additional findings led to a change in management in 43 out of the 131 (32.8%) of patients. Given the clear imaging superiority of ⁶⁸Gallium-DOTATATE PET/CT to Octreoscan, we will no longer perform Octreoscan in patients being enrolled and will compare its accuracy to CT/MRI scanning. This will result in lower radiation exposure to subjects and reduced cost.

8 COLLABORATIVE AGREEMENTS

There are MTA agreements under negotiation for the study referenced in section 5.1.4 with:

UCSF (pending)

UCLA (pending)

9 HUMAN SUBJECTS PROTECTIONS

9.1 RATIONALE FOR SUBJECT SELECTION

Patients with suspicious neuroendocrine lesions, unknown primary tumor or metastatic gastrointestinal or pancreatic neuroendocrine disease found on anatomic imaging (CT/MRI) or patients with biochemically active disease will be selected for this study. Both functional and non-functional solid tumors will be included in this study. Furthermore, asymptomatic and symptomatic, and both sporadic and familial cases of NETs (such as VHL, MEN1) will be included who have biochemical or anatomic imaging evidence of disease. Patient selection for this protocol will not be based on gender, race or ethnic background.

9.2 PARTICIPATION OF CHILDREN

Children below the age of 10 will not be included on this protocol. Only patient age 10 and older will be eligible for this study because no dosing or adverse event data are currently available on the use of ⁶⁸Gallium DOTATATE in patients younger than 10 years of age. Therefore, children under 10 are excluded from this study.

9.3 PARTICIPATION OF SUBJECTS UNABLE TO GIVE CONSENT

In cases where the patient is unable to give informed consent, an appropriate surrogate, such as a DPA, will be identified as per the NIH Clinical Center (CC) MAS M87-4 policy. In that case, members of the protocol team will describe the protocol, alternative therapies, and the risks and benefits of each to the patient's DPA for health care and the DPA may give informed consent on behalf of the patient. If possible, signed assent will be obtained from patients unable to give informed consent. For NIH CC patients, the assent signature line at the end of NIH form 2514-1 will document such assent. As patients may be cognitively impaired due to brain metastases, and a DPA is being used because the patient is unable to understand the consequences of their assent or dissent, the Study PI has determined that the designated DPA should be allowed to make the decision for the patient to enroll in this protocol. In cases where the patient's DPA is unable to be present in person at the Clinical Center, obtaining informed consent via technology and/or electronic processes is permissible. In these cases, the informed consent discussion will be carried out over telephone and giving of informed consent may be done by phone, fax or email. The informed consent process will be documented in the patient's medical record and on the informed consent document. This process will be performed by the local Principal Investigator or designee.

Re-consent may be necessary and there is a possibility, though unlikely, that subjects could become decisionally impaired. For this reason and because there is a prospect of benefit from research participation (section 9.4), all subjects ≥ 18 years old will be offered the opportunity to fill in their wishes for research and care, and assign a substitute decision maker on the "NIH Advance Directive for Health Care and Medical Research Participation" form so that another person can make decisions about their medical care in the event that they become incapacitated or cognitively impaired during the course of the study. Note: The PI or AI will contact the NIH Ability to Consent Assessment Team for evaluation. For those subjects that become incapacitated and do not have pre-determined substitute decision maker, the procedures described in NIHMEC Policy 87-4 for appointing a surrogate decision maker for adult subjects

Abbreviated Title: ⁶⁸Gallium Detecting Tumors

Version Date: 09/20/17

who are (a) decisionally impaired, and (b) who do not have a legal guardian or durable power of attorney, will be followed.

9.4 EVALUATION OF BENEFITS AND RISKS/DISCOMFORTS

There is no direct benefit for patients participating in this study but if the study results show ⁶⁸Gallium-DOTATATE PET/CT imaging to be more accurate, the future application of this imaging modality in other patients could lead to early detection of solid gastrointestinal or pancreatic lesions and early management of these lesions, which may have an impact on the overall course of the disease. This study also offers the benefit of surgery, when patients meet the criteria for resection, in an institution with vast experience with patients who have NETs.

Risks and discomforts of the experimental procedure are expected to be low and related to the risks of ⁶⁸Gallium-DOTATATE, and SPECT/CT imaging. Most complications are expected to be minor and require no treatment.

Risks and discomforts associated with ⁶⁸Gallium-DOTATATE PET/CT imaging are discomfort of an IV placement and the theoretical effects of the amount of additional radiation exposure. The effective dose for adults per PET/CT scan with 5.0 mCi of ⁶⁸Ga-DOTATATE administered activity is 1.1 rem per year or 1.6 rem if receiving two ⁶⁸Ga-DOTATATE injection of 5.0 mCi of ⁶⁸Ga-DOTATATE in case of surgery, which in both cases is below the maximum of 5.0 rem per year recommended by the radiology safety guidelines for adult research subjects. The effective dose for children over 15 per PET/CT scan with 5.0 mCi of ⁶⁸Ga-DOTATATE administered activity is 0.30 rem per year or 0.40 rem if receiving two ⁶⁸Ga-DOTATATE injection of 5.0 mCi of ⁶⁸Ga-DOTATATE in case of surgery, which in both cases is below the maximum of 5.0 rem per year recommended by the radiology safety guidelines for adult research subjects. The effective dose for children between 10 and 14 per PET/CT scan with 5.0 mCi of ⁶⁸Ga-DOTATATE administered activity is 0.35 rem per year or 0.45 rem if receiving two ⁶⁸Ga-DOTATATE injection of 5.0 mCi of ⁶⁸Ga-DOTATATE in case of surgery, which in both cases is below the maximum of 5.0 rem per year for adult research subjects and 0.5 rem per year for children research subjects recommended by the radiology safety guidelines for adult research subjects. In this study, the subject will be required to lie still on his back for around 30 minutes during image acquisition in the PET/CT scanner, and this might produce some discomfort.

Risks associated with the surgical procedures to manage lesions in the pancreas will vary based on the type of lesion and the planned surgical procedure and are part of standard clinical care. These risks will be discussed in depth on a patient-by-patient basis.

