3.3 STUDY CALENDAR

	Screening	Baseline	Day of PET/CT	Dose	PET/CT Imaging	Yearly Follow-Up
Informed consent	•					
Study entry criteria	•					
Demographic information	•					
Medical history and concurrent diseases	•					
Prior/concomitant medication	•					
Physical examination	•					
Vital signs ^a	•					
Blood samples		• ^b				• ^c
AE Monitoring/Query						•

	Screening	Baseline Day of PET/CT	Dose	PET/CT Imaging	Yearly Follow-Up
⁶⁸ Ga-DOTATATE administration ^d			•		• ^e
⁶⁸ Ga-DOTATATE PET/CT Imaging				•	• ^e
CT Imaging ^f	•				•
Correlative Research Studies			• ^g		
Advance Directive ^h		•			

^a Vital signs: Heart rate, blood pressure, respiratory rate, temperature, pulse oximetry (according to Appendix A and B).

^b At screening: CBC with differential/ Full chemistry/ Neuroendocrine peptides (as cited in section **3.1.1.3**)/ Pregnancy test if required.

^c At yearly follow-up if functional tumors: Fasting insulin, glucagon, VIP, pancreatic polypeptide, neuron specific enolase, urinary 5-HIAA, catecholamines, metanephrines, fasting chromogranin A fasting gastrin

^d Administration of about 5mCi of the ⁶⁸Ga-DOTATATE intravenously.

^e To be performed at the one year follow up time point and up to 5 years from study enrollment in certain patients only.

^f To be performed within ± 6 months of the ⁶⁸Ga-DOTATATE PET/CT.

Abbreviated Title: ^{68}Ga Gallium Detecting Tumors
Version Date: 09/20/17

^g Correlative Research Studies: Blood and urine sample as described in section **4.1**.

^h Filling out of the advance directive will be offered, but obtaining of it is not required. For details see Section **9.3**.

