3.4 SURGICAL MANAGEMENT

After their initial on-study evaluation, patients will be staged according to findings on imaging studies with respect to primary tumor site, size and metastases. Surgical resection of NET and/or medical managements will be recommended based on standard practice guidelines [58].

Surgery will be recommended to manage lesions within the gastrointestinal tract and pancreas under the following circumstances:

3.4.1 Patients with solid lesions that are thought to be NETs by non-invasive imaging studies will be considered for surgery if:

- Their solid lesion is enlarging on serial imaging studies.
- Their solid lesion is associated with symptoms consistent with gastrointestinal or pancreatic NET.
- A solid lesion in the head of the pancreas is ≥ 2 cm in size.
- A solid lesion in the body or tail of the pancreas is ≥ 3 cm in size.
- Gastrointestinal functional tumors will be treated according to standard clinical practice.
- Metastases will be addressed according to standard clinical practice.

3.4.2 Patients who present with evidence of cardiac risk factors will undergo a cardiac evaluation prior to surgical intervention according to standard clinical practice.

3.4.3 In patients who require an operation and have ⁶⁸Ga-DOTATATE uptake on PET/CT, a radio-guided surgery will be performed using a hand-held gamma probe. These patients will get a ⁶⁸Ga-DOTATATE injected 1.5 to 2 hours before the time of the operation. A dose of 5 mCi of ⁶⁸Ga-DOTATATE will be injected. During the surgical procedure, lesions will be localized using the gamma probe with comparison of target lesion activity to non-target tissue activity as uptake of ⁶⁸Ga-DOTATATE in normal tissues could be variable.

For patients undergoing surgical resection, tissue that is removed will be analyzed in the Surgical Pathology Department to confirm diagnosis, and with the patient's consent, a small part of the resected tissue will be used for research purposes (as described in section **1.1** and section **4.1**). After procurement for the Surgical Pathology Department, we will collect at least 0.5x0.5x0.5 cm of tissue sample that remains.

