3.5 STANDARDIZED ⁶⁸GA-DOTATATE PROTOCOL

Fasting is not required prior to the imaging study. An IV line with a large bore (21 gauge or more) will be placed preferably in the antecubital vein, and, with the patient supine, around 5mCi of the ⁶⁸Ga-DOTATATE will be administered intravenously, followed by incubation for approximately 60 minutes. Then the patient will be positioned in a PET/CT scanner and images from the upper thighs to the base of the skull will be obtained. In patients with tumor induced osteomalacia, images from the top of the head to the toes will be obtained.

To date, there are no known allergic reactions to ⁶⁸Ga-DOTATATE.

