10.1.5 Administration procedures

[⁶⁸Ga]DOTATATE will be administered intravenously in conjunction with the PET/CT scan. The one-time nominal injected dose will be 5 mCi in a volume of 3 - 5 ml containing up to 50 µg [⁶⁸Ga] DOTATATE.

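### Section 9.4 gives adults and children the same 5.0 mCi per injection, yet the second injection adds 0.50 rem in adults and 0.10 rem in children, so compliance with the 0.5 rem paediatric limit is unsupported as written

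*Combined protocol and SAP*

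**What the plan says.** Section 9.4 gives annual effective doses for three age groups, each at 5.0 mCi per injection. The first figure is for one PET/CT scan; the second is for a patient who also has surgery and so receives two injections.

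- Adults: "administered activity is 1.1 rem per year or 1.6 rem if receiving two" injections, compared with a limit of 5.0 rem per year.
- Children over 15: "administered activity is 0.30 rem per year or 0.40 rem if receiving two" injections, compared only with the 5.0 rem adult limit.
- Ages 10 to 14: "administered activity is 0.35 rem per year or 0.45 rem if receiving two" injections, compared with the adult limit and with "0.5 rem per year for children research subjects". Both doses are said to be below these limits.

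The second injection is described in section 3.4.3. It is "injected 1.5 to 2 hours before the time of the operation. A dose of 5 mCi of" the tracer, used with a hand-held gamma probe; no second PET/CT is described. The other dosing sections agree on the activity and none gives a separate figure for children: section 3.3 has "Administration of about 5mCi of the" tracer, section 3.5 has "with the patient supine, around 5mCi of the" tracer, and section 10.1.5 says the "nominal injected dose will be 5 mCi in a volume of 3 - 5 ml".

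Patients aged 10 and over are eligible (sections 2.1.1.2 and 9.2). Section 10.1.2 advises careful evaluation before use in anyone under 18.

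**The concern.** If two groups receive the same activity and the second injection involves no further CT, the step from the one-injection to the two-injection dose is the tracer dose of that activity. One would not expect it to be five times smaller in a child than in an adult. Section 9.4's own one-scan totals rise from the older to the younger child group (0.30 to 0.35 rem), yet the adult total is 1.1 rem.

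What is at stake is a paediatric radiation limit. The figures for ages 10 to 14 are the plan's only stated comparison with 0.5 rem per year, and with surgery the printed margin is 0.5 − 0.45 = 0.05 rem. Subjects aged 16 and 17 are also children, but their doses are not set against that limit at all.

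**Working it through.** **Inputs** (section 9.4, rem per year, 5.0 mCi per injection in every group): adults 1.1 and 1.6; over 15, 0.30 and 0.40; ages 10 to 14, 0.35 and 0.45. Paediatric limit 0.5.

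**Step 1. Dose added by the second injection** = two-injection dose − one-injection dose; dose per mCi = step / 5.0; remainder = one-injection dose − step.

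| Group | Step (rem) | Per mCi (rem) | Non-tracer remainder (rem) |
|---|---|---|---|
| Adults | 1.6 − 1.1 = 0.50 | 0.10 | 1.1 − 0.50 = 0.60 |
| Over 15 | 0.40 − 0.30 = 0.10 | 0.02 | 0.30 − 0.10 = 0.20 |
| 10 to 14 | 0.45 − 0.35 = 0.10 | 0.02 | 0.35 − 0.10 = 0.25 |

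The printed 0.45 rem is reproduced (0.25 + 2 × 0.10) only if 5.0 mCi delivers 0.10 rem. The adult figures imply 0.50 rem for the same activity. Ratio: 0.50 / 0.10 = 5.0.

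**Step 2. Could rounding explain it?** Suppose adult doses are rounded to 0.1 rem and child doses to 0.05 rem (an assumption, coarser than the two decimals printed for children). The adult step is then at least 1.55 − 1.15 = 0.40 rem. The child step is at most 0.10 + 2 × 0.025 = 0.15 rem. The ratio is still at least 0.40 / 0.15 = 2.7.

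**Step 3. Could the second figure be a repeated full scan?** Doubling the one-scan doses gives 2.2, 0.60 and 0.70 rem. The printed values are 1.6, 0.40 and 0.45, so no.

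**Step 4. Could children receive a lower activity?** If the adult coefficient held in children (assumption), a 0.10 rem step would correspond to 0.10 / 0.10 = 1.0 mCi. Section 9.4 prints 5.0 mCi, so on this reading the printed activity is the error.

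**Step 5. How much would the paediatric dose have to change to matter?** Let t be the tracer dose per injection. Assume it is equal for both injections, that there is no second CT, and that the remainder in step 1 is right.

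- Ages 10 to 14, scan plus surgery: 0.25 + 2t = 0.5 gives t = 0.125 rem, 25% above the implied 0.10. The adult step is 0.50 / 0.125 = 4.0 times this.
- Over 15, scan plus surgery: 0.20 + 2t = 0.5 gives t = 0.15 rem, 50% above the implied 0.10. The adult step is 0.50 / 0.15 = 3.3 times this.
- Scan alone: t = 0.25 rem (10 to 14) and 0.30 rem (over 15).

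The documents give no age-specific coefficient, so for ages 10 to 14 here is the range from the implied child value to the full adult value:

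| t as a share of the adult step | t (rem) | Scan alone, 0.25 + t | Scan plus surgery, 0.25 + 2t |
|---|---|---|---|
| 20% (as printed) | 0.10 | 0.35 | 0.45 |
| 25% | 0.125 | 0.375 | 0.50 |
| 30% | 0.15 | 0.40 | 0.55 |
| 50% | 0.25 | 0.50 | 0.75 |
| 100% | 0.50 | 0.75 | 1.25 |

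If only the second injection is recosted at the adult value, the total is 0.35 + 0.50 = 0.85 rem.

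**The case against.** The strongest reply is that the figures are unexplained rather than wrong. Section 9.4 does not say what its totals contain, so the adult two-injection figure might include a CT allowance. The documents give no age-specific coefficients that would rule out a lower child dose. Sections 10.1.1 and 10.1.3.2 have the tracer ordered by a physician and prepared to a prescribed activity, so children may in practice receive less than 5 mCi, with correct doses beside a copied-over activity. A dose breakdown may also sit in a radiation authorisation, the IND or the consent pages, which are outside the text available here, as is the follow-up section.

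None of this rescues section 9.4 as printed. It attributes the step to a second injection, and section 3.4.3 describes no further scan; an unstated CT allowance for adults alone would contradict both. A reduced paediatric activity would make the printed 5.0 mCi wrong for children.

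Several limits do stand. A breach is not shown. The break-even values start from child figures that may themselves be wrong, so they are illustrative. The over-15 doses as printed (0.30 and 0.40 rem) would pass the 0.5 rem limit. The narrow margin concerns only a child who has both a scan and radio-guided surgery within a year, and no efficacy endpoint or sample size is affected.

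**Conclusion.** The concern holds. At one stated activity, section 9.4 credits the second injection with 0.50 rem in adults and 0.10 rem in both child groups. At least one printed activity or dose is therefore wrong: the adult doses, the child doses or the activity stated for children. This rests on two premises: that the step is tracer dose only, as sections 9.4 and 3.4.3 describe it, and that equal activity does not deliver one fifth of the dose to a smaller body.

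The statement that ages 10 to 14 stay below 0.5 rem per year is unsupported as written. Under the assumptions in the working, a tracer dose 25% above the implied value would bring scan plus surgery to the limit. Because a paediatric safety limit with a printed margin of 0.05 rem depends on it, this must be fixed.

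**What to change.** 1. Verify the activity actually given, or to be given, in each age group.
2. Recompute the effective dose per group from that activity, showing tracer and CT separately, for a scan alone and for a scan plus surgery.
3. Compare every subject under 18 with the 0.5 rem limit, including those over 15. Close the gap at age 15, which falls in neither child band.
4. Correct whichever figure in section 9.4 is wrong.
5. If children receive less than 5 mCi, state the paediatric activity in sections 3.3, 3.4.3, 3.5 and 10.1.5 as well.

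The cost is a dosimetry check and a text correction in section 9.4, plus a line in each dosing section if the paediatric activity differs. The corrected paediatric risk statement may be less favourable than the present one.
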